**Participant Compensation**

Compensation will be according to each site's acceptable local policy, i.e. gift cards or (ETF) electronic transfer of funds, etc. Compensation will be based on study visit time and effort and to help with transportation/parking costs. PNES and ES participants will receive up to a total of \$800 for study involvement. Compensation will be \$100 per fMRI (for scan and testing/tasks at the fMRI session) which will be given after the completion of the fMRI and up to \$600 at the last CBT-Sz session (\$50 for completion of each of the 12 sessions).

The TBI controls will receive up to \$200 for their time and effort. They will receive \$100 for each fMRI session (for scan and testing/tasks at the fMRI session) which will be given after the completion of the fMRI.

**4.0 Data Analysis**

Each site will administer, score, code and enter the data. Evaluators will be trained in the administration of the scales and cross-site interrater reliability will be established in the startup phase. Staff will enter identifiable behavioral, demographic, and other non-neuroimaging data in the secure site REDCap hosted at RIH through participant permission (HIPAA). Neuroimaging data will be transferred to a secure site hosted at UAB (behind firewall) via secure uplink and/or by secure shipment of the imaging disc that will include the participant's study code and date of the fMRI.

**4.1 Power analysis**

Our power analysis is based on our preliminary neuroimaging and clinical data, and data regarding number needed to be evaluated in neuroimaging studies to reliably demonstrate differences between

groups in cognitive studies. Based on our preliminary data for the fMRI stress task ([name], unpublished), given the large effect size (Cohen's *d*) of 0.88, when the sample size is 14 people per group, a *t*-test of two related samples with 5% two-sided significance will have about 85% power to reject the null hypothesis that there is no difference in pre-intervention and post-intervention fMRI measures in limbic structures (medial frontal cortices and amygdala). In a recently analyzed study of the emotional faces fMRI task, 12 participants per group were sufficient to show significant differences between participants with PNES, ES and controls in emotion control brain circuits. ([name], et al, HMB, under review) It is possible that the effect size may not be as large in ES as it is expected in PNES. For this study, we expect 25 participants per group to be sufficient to account for the possibility of a more conservative effect size (e.g., 0.65). With the expected 50% responder rate to the cognitive challenge (CBT-Sz), 50 per each group (PNES, PTE, controls) will allow to test the within groups and between groups differences. Adding additional 24 participants per group will allow controlling for two most frequent comorbidities in our patients (12/condition; depression / anxiety and PTSD; 50+24=74). With anticipated attrition rate of up to 20% ( $74 \times 0.2 = 14$  to 15 per group) a sample of 88 Veterans with PNES, 88 Veterans with PTE, and 88 Veterans with TBI but no PNES/PTE can address the study hypotheses and control for the confounders including comorbidities.

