## **OBJECTIVES**

We will investigate:

1. Differences in cerebral underpinnings of emotion and stress processing in PNES and PTE using well established fMRI probes.
2. Neuroimaging biomarker of PTE and PNES that predicts treatment outcome in order to inform effective non-pharmacologic treatments for seizures; and
3. Evidence for a positive treatment response to the intervention (CBT-Sz) that results in neuroplasticity – i.e., the symptom change instantiated by actual physiologic change in the brain.

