## **STUDY DESIGN OVERVIEW**

Our plan is to investigate the cerebral underpinnings of emotion and stress processing in 88 individuals with confirmed PNES and 88 individuals with confirmed PTE and 88 individuals with a history of TBI without seizures (PNES or PTE) matched for psychiatric comorbidities (TBI control subjects – CS). In addition to the between group comparisons (PNES vs. PTE vs. CS), we will examine the changes in brains' response to fMRI probes after receiving treatment (CBT-Sz), a non-pharmacologic therapeutic approach that is used for the treatment of difficult to control seizures in patients with PNES and PTE. All participants in the 3 groups will receive fMRI scans at approximately 13 week intervals. Including CS in the neuroimaging and symptom surveys portion will allow us to determine the stability of signals between and within the individuals and to control for the effects of psychological and psychiatric comorbidities.

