### **Imaging data analyses**

We will employ a multilevel approach to data analysis (1) image analysis (post-processing), (2) statistical hypothesis testing and modeling using summary imaging measures and clinical variables (these two analyses will use a summary parameterization of the fMRI and DTI data, which are the presence or absence of activation within the prescribed regions of interest (ROIs) defined for each modality (e.g., amygdala or medial prefrontal cortex for fMRI data) or integrity of white matter tracts connecting amygdala and medial frontal regions (e.g., number of white matter fibers or FA values) which will be based on the composite MRI data, and (3) image analysis that allows for modeling changes over time while considering the effect of covariates in hierarchical linear modelling (HLM). Our analyses will be corrected for multiple comparisons at a  $p < 0.05$  level to limit the possibility of false positives while maintaining sufficient power to detect effects of interest.

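### Section 4.1 requires 74 per group after up to 20% attrition, but 88 per group leaves about 70, and no power calculation supports its claim that 50 per group can test between-group differences.

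*Combined protocol and SAP*

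**What the plan says.** Section 4.1 builds the sample size in steps.

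- **Paired test.** With Cohen's d of 0.88 on the fMRI stress task and 14 people, a t-test of "two related samples with 5% two-sided significance will have about 85% power" to detect pre/post change in limbic structures.
- **Smaller effect.** "It is possible that the effect size may not be as large in ES as it is expected in PNES", and "we expect 25 participants per group to be sufficient to account for the possibility of a more conservative effect size (e.g., 0.65".
- **Responders.** With an expected 50% responder rate to CBT-Sz, 25 becomes 50, and "50 per each group (PNES, PTE, controls) will allow to test the within groups and between groups differences".
- **Comorbidities.** A further 24 per group brings the total to 74.
- **Attrition.** "With anticipated attrition rate of up to 20" per cent, 14 to 15 per group are added, which gives 88 per group (264 in all).

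The only between-group support in section 4.1 is that 12 per group showed differences between PNES, ES and controls in an earlier emotional faces study.

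Elsewhere, the first Objective is "Differences in cerebral underpinnings of emotion and stress processing in PNES and PTE using well established fMRI probes". The Study Design Overview plans "between group comparisons (PNES vs. PTE vs. CS". Hypothesis 1 (Specific Aims) places the group differences at baseline. The imaging data analyses paragraph after section 4.1 states: "Our analyses will be corrected for multiple comparisons".

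**The concern.** An allowance for attrition should leave the required number when attrition reaches the stated ceiling. Here it does not, although section 4.1 concludes that 88 per group is enough for the hypotheses and the confounders.

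The second gap is that a paired pre/post calculation says nothing direct about a comparison between groups. A two-sample comparison has a different standard error and needs its own effect size and SD, and neither is stated. The calculation also uses an uncorrected 5%, while the analysis is to be corrected for multiple comparisons. If between-group power is taken as established when it has not been, a non-significant PNES v PTE comparison could be misread as showing that the two disorders respond alike.

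A smaller point concerns the doubling from 25 to 50. It rests on response to CBT-Sz but is applied to the controls too, who receive no CBT-Sz (sections 3.1 and 3.6).

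**Working it through.** **Inputs from section 4.1:** d = 0.88 with n = 14; d = 0.65 with n = 25; two-sided 5%; 50% responders; 74 required per group; attrition up to 20%; 88 enrolled per group. The documents give no SD of change for any group and no between-group effect size. t-test power below is from the noncentral t distribution.

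**1. The plan's own figure.** Paired test, noncentrality d × √n, n − 1 degrees of freedom.
- n = 14, d = 0.88: 0.88 × √14 = 3.29, power 86.0%. This reproduces the stated figure of about 85%.
- n = 25, d = 0.65: 0.65 × √25 = 3.25, power 87.6%. This step is adequate for a paired test. As a two-sample test with 25 v 25, the same d has 61%.

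**2. Attrition.**
- The plan's step: 74 × 0.2 = 14.8, so 14 to 15 are added; 74 + 14 = 88.
- What remains at 20%: 88 × 0.8 = 70.4, which is 3.6 per group below 74 (3 × 3.6 = 10.8, about 11 in total).
- What 74 would need: 74 / 0.8 = 92.5, so 93 per group and 3 × 93 = 279 in total.
- Largest attrition at which 88 still leaves 74: 1 − 74/88 = 15.9%.

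**3. Between-group power, as a conditional illustration only.** Assume that 0.88 is the PNES effect, 0.65 the PTE effect, the SD of change is equal in all groups, and the measure is continuous. Two-sample test with noncentrality d / √(2/n), uncorrected 5%.

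| Contrast in change | d | 50 per group | 70 per group |
|---|---|---|---|
| PNES v PTE | 0.88 − 0.65 = 0.23 | 20.7% | 27.2% |
| PTE v controls with no change | 0.65 | 89.6% | 96.9% |
| PNES v controls with no change | 0.88 | 99.2% | 99.9% |

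80% power at d = 0.23 would need 298 per group.

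**4. Sensitivity of the PNES v PTE row.**
- If the PTE SD of change is k times the PNES SD, d = (0.88 − 0.65k) / √((1 + k²)/2). At k = 0.8, d = 0.398 and power is 50% at 50 per group and 65% at 70. At k = 1.25, d = 0.060 and power is about 6% at both sizes.
- If the PTE effect is 0.50 (difference 0.38), power is 47% at 50 and 61% at 70. If it is 0.40 (difference 0.48), power is 66% and 81%.

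**5. What the sample can detect (80% power, uncorrected 5%).**
- Change, 70 per group: 0.477 SD.
- Baseline, 88 per group: 0.425 SD.
- At alpha 0.0125, assumed here only to show the effect of correction, these become 0.57 and 0.51 SD.
- 95% CI half-width for a difference in change, 70 v 70: 1.977 × √(2/70) = 0.334 SD.

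**The case against.** A reader might infer that the plan's own effect sizes imply 21% power for PNES v PTE. The documents do not support that. Section 4.1 does not assign 0.88 to PNES. The 0.65 is an example of a possible conservative effect, not an expected PTE effect. Subtracting one from the other requires equal SDs of change, which are not given, and step 4 shows how far the answer moves without them. Nor is PNES v PTE in change a named hypothesis. Hypothesis 1 is about baseline, and Hypothesis 2 is about change in the seizure participants and its relation to clinical response. Specific Aim 1 sets before/after responses in the seizure groups against controls, and on the same assumptions that contrast has about 90% to 99% power at 50 per group. All of this stands, so the 21% is an illustration and not a finding about the trial.

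On attrition, 20% is an upper bound, and section 4.3 asks participants who stop CBT-Sz to attend the second scan, so stopping therapy need not lose the scan. The loss is also small: the detectable difference in change moves from about 0.465 SD at 74 to 0.477 SD at 70, and baseline comparisons are not affected by later dropout. This limits the consequence but does not remove the slip, because a plan that allows for up to 20% should hold at 20%.

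The earlier faces-task result is some support for between-group differences. It is a past significant finding, reported without an effect size, and does not amount to a power calculation. Finally, no passage says that a null result will be read as equal response; the rule proposed below is a precaution.

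**Conclusion.** Two statements hold without any added assumption. At the stated ceiling of 20% attrition, 88 per group leaves about 70, not 74. And the claim that 50 per group covers between-group differences has no between-group effect size, SD or power behind it; the one calculation shown is paired, within group and uncorrected.

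How much power there is between groups cannot be settled from the documents. For change, the two effect sizes give anything from about 21% to 99% at 50 per group, depending on the contrast, and only under the assumptions in step 3. For the baseline contrasts of Hypothesis 1, pre/post effect sizes give no answer. The two-sample t-tests here are also simpler than the planned analyses, which include presence or absence of activation and hierarchical linear models with covariates.

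The point warrants correcting the text of section 4.1. It does not show that the trial is too small for its stated hypotheses.

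**What to change.** In section 4.1:

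1. Keep 88 per group and restate the target as 70 per group after 20% attrition. If 74 are truly needed, enrolment would have to be 93 per group (279 in total, 279 − 264 = 15 more).
2. Replace the between-group claim with the differences detectable at 80% power: about 0.48 SD for change at 70 per group and 0.43 SD at baseline at 88 per group. Label these as uncorrected, and restate them at the corrected alpha once the number of tests is fixed.
3. Prespecify that PNES v PTE change is reported as an estimate with its 95% CI (half-width about 0.33 SD at 70 v 70 for a continuous measure), and that a non-significant result will not be read as equal response.
4. Justify the number of controls by the purposes in the Study Design Overview (signal stability, control for comorbidities) and by the baseline comparison, not by the CBT-Sz responder rate.

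The cost is rewording and one rule of interpretation. The stated figures become slightly less favourable. No extra participants are needed if the target is restated as 70.

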## **SPECIFIC AIMS**

**Specific Aim 1:** To compare neural correlates of response to fMRI stimuli before and after cognitive challenge (CBT-Sz). Individuals with PNES and PTE will be compared to individuals with a history of TBI who do not have PTE/PNES in order to control for common comorbidities including depression, anxiety and PTSD, and to show fMRI signal stability between and within the individuals.

**Hypothesis 1:** We hypothesize, based on our preliminary data, that baseline fMRI in all groups will show aberrant responses to stress and abnormal emotional processing between those with seizures vs. those without seizure disorders, with differences predominantly observed in the medial frontal cortices and amygdala with these differences being most abnormal in the PNES group.

**Specific Aim 2:** To investigate changes in neural circuitry for emotional processing in individuals with seizures after receiving CBT-Sz and to correlate these changes with symptomatic improvement.

**Hypothesis 2:** We hypothesize that CBT-Sz will lead to changes in the fMRI signals and in amygdala connectivity as shown with DTI and fMRI. This change will, in turn, be predicted by the magnitude of clinical responses defined by seizure frequency improvement over time and secondarily by targeted behavioral measures.

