## **Functional imaging in epilepsy and PNES**

Pathological responses to stressors are the origin of Conversion Disorders (CDs), which are thought to be related to “repression of psychological conflict and its conversion into physical” symptoms. Neuroimaging investigations of pathophysiologic mechanisms underlying CDs and PNES or epilepsy are scarce. In a motor CD study the authors explained the observed differences between patients with CD and comparable participants without CD as different utilization of emotion and stress neural circuits for processing stressful lifetime events. Another study showed greater FC between right amygdala and right supplementary motor cortex indicating a possible mechanism underlying motor CD. We recently compared emotion processing in patients with epilepsy and PNES without the preexisting TBI or without introducing an intervention ([name] et al., HBM under review). We have shown that compared to ES, that patients with PNES exhibit increased fMRI response to happy and neutral emotions in cerebellar and fronto-temporo-parietal regions and to fear in bilateral inferior and middle temporal gyri and right middle occipital gyrus. Connectivity analyses comparing patients with PNES and ES identified substantial differences in functional connectivity to several brain regions, particularly to cerebellar, visual, and fronto-temporal regions. Resting state connectivity of the left and right amygdala to various brain regions including emotion regulation circuits was increased in patients with PNES when

compared to patients with ES. Additional analyses showed aberrant functional connections between left uncus and right hemispheric regions in PNES compared to both the ES and healthy control groups. In summary, we documented that patients with PNES exhibit altered emotion processing and increased amygdala functional connectivity compared to ES. These findings identified key differences in emotion processing reflective of potential neurophysiologic markers of neural circuitry alterations in PNES with their presence possibly underlying initiation and/or maintenance of PNES when compared to ES.

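### Does doubling 25 to 50 per group for a 50% responder rate leave the within-group and between-group tests in section 4.1 unsupported?

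*Combined protocol and SAP*

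**What the plan says.** Section 4.1 starts from preliminary stress-task data with d = 0.88 and 14 people per group. It names a t-test "of two related samples with 5% two-sided significance will have about 85% power" against the null hypothesis of "no difference in pre-intervention and post-intervention fMRI measures in limbic structures". For between-group evidence it reports that in a faces-task study "12 participants per group were sufficient to show significant differences between participants with PNES, ES and controls"; its opening sentence also cites published work on the numbers needed in group neuroimaging studies.

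It then allows for a smaller effect in epilepsy than in PNES: "we expect 25 participants per group to be sufficient to account for the possibility of a more conservative effect size (e.g., 0.65". Neither the test nor the power is restated there. Next comes the expected 50% responder rate, and the conclusion that "50 per each group (PNES, PTE, controls) will allow to test the within groups and between groups differences". A further 24 per group for comorbidities gives 74, and allowance for up to 20% attrition gives 88.

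Other sections bear on this. Under section 3.1 only the PNES and PTE groups receive CBT-Sz. In Specific Aims, Hypothesis 1 is a baseline contrast between groups. Aim 2 concerns people with seizures after CBT-Sz, and Hypothesis 2 relates brain change to the size of the seizure improvement. Imaging data analyses plans hierarchical linear modelling of change over time with covariates. Section 4.3 asks participants who do not start or finish CBT-Sz to have the second scan anyway.

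**The concern.** Dividing by a responder rate makes direct sense for one analysis: a pre/post test among responders alone. No section plans that analysis, and it would select participants on a post-treatment outcome. If instead 0.65 is the effect in responders and everyone treated is analysed, the average effect is roughly halved, and the sample must grow by about 1/r² rather than 1/r: 25 / 0.25 = 100, not 50.

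Two features add to the impression of a faulty step. The responder rate is applied to untreated controls. And the sentence claims between-group tests although the only test named is within-group. The 12-per-group study appears to be the one described under Functional imaging in epilepsy and PNES ("We recently compared emotion processing in patients with epilepsy and PNES without the preexisting TBI or without introducing an intervention"). If so, it says nothing about between-group change after treatment, which matters because Aim 1 is "To compare neural correlates of response to fMRI stimuli before and after cognitive challenge (CBT-Sz").

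At stake is whether 88 per group can be said to address the hypotheses, and whether the wording invites a responder-only analysis of Aim 2.

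**Working it through.** **Inputs.** From section 4.1: d = 0.88 with n = 14; d = 0.65 with n = 25; responder rate r = 0.5; 50 per group; attrition up to 20%, so 88 × 0.8 = 70.4, about 70 evaluable per group. Two-sided 5% is stated for the first step and used throughout, with no multiplicity correction. Zero or partial change in non-responders is an assumption; the documents give no figure.

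**Formulas.** Noncentral t. Paired test: noncentrality d√n, n − 1 degrees of freedom. Two groups of n: noncentrality d√(n/2), 2n − 2 degrees of freedom.

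**The plan's own chain**
- n = 14, d = 0.88: noncentrality 0.88 × √14 = 3.29, power 86.0%. The plan says about 85%.
- n = 25, d = 0.65: noncentrality 0.65 × 5 = 3.25, power 87.6%. For 85%, n = 24 is enough.
- 25 / 0.5 = 50.

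Every stated figure reproduces. The plan states no power for the 25 or the 50, so there is no figure for these steps to miss.

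**Within-group change, by reading of 0.65**
- All-treated effect, n = 50: 99.5%. The doubling is then a surplus.
- Responder effect, tested in about 25 responders: 87.6%.
- Responder effect, all treated analysed, non-responders unchanged (assumption): mean change 0.5 × 0.65 = 0.325; SD = √(1 + 0.25 × 0.65²) = 1.051; d = 0.325 / 1.051 = 0.309. Power is 57% at 50 and 72% at 70. With PNES and PTE pooled (2 × 70 = 140) it is 95%.
- The same, with non-responders changing a quarter as much (assumption): mean 0.65 × (1 + 0.25) / 2 = 0.406; SD = √(1 + 0.25 × 0.4875²) = 1.029, where 0.4875 = 0.75 × 0.65; d = 0.395. Power is 78% at 50 and 90% at 70.

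**Between-group differences**
- Baseline contrast, if d = 0.65: 89.6% at 50 v 50 and 96.8% at 70 v 70.
- Change v controls, responder reading, non-responders unchanged: 35% at 50 v 50 and 46% at 70 v 70.
- Change v controls, non-responders changing a quarter as much: 51% and 65%.

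The baseline figures borrow a d that was set for paired change. The paired and two-sample scales agree only at a pre/post correlation of 0.5. At 0.7 (assumption), 0.65 becomes 0.65 × √(2 × 0.3) = 0.50, and power is 70% at 50 v 50 and 84% at 70 v 70. The baseline contrast is therefore plausible at the planned size but not proved.

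**The case for a change.** The best case for a change is this. Section 4.1 is where the plan argues that 88 per group can address its hypotheses, yet it contains no calculation for between-group change. On the reading that the responder step itself suggests, that comparison could have 35% to 46% power. A few sentences would settle the matter at no cost in participants.

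Part of this stands. The plan does not say whose effect 0.65 is or which population the doubling serves, and it gives no power for between-group change.

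The rest does not carry:
- **The low figures need two added assumptions.** Section 4.1 brings in 0.65 because the effect may be smaller in epilepsy than in PNES; it does not tie it to responders. Nor does it say that non-responders show no change.
- **The sentence claims differences, not differences in change.** That can include the Hypothesis 1 baseline contrast, to which an untreated three-group comparison is relevant. The 12-per-group study is also not the only between-group support offered, since the opening sentence cites neuroimaging sample-size work that cannot be assessed from the documents.
- **A responder v non-responder contrast is not planned.** At 25 v 25 and d = 0.65 it would have 61% power. The objective of finding a "Neuroimaging biomarker of PTE and PNES that predicts treatment outcome" does not require it, and Hypothesis 2 uses the magnitude of response.
- **A responder-only Aim 2 is largely ruled out already.** Aim 2 covers people with seizures after CBT-Sz, no responder set is defined, and section 4.3 seeks second scans from non-completers.
- **The binary activation summary and the multiplicity correction are separate matters.** The presence-or-absence summary belongs to the first two analysis levels; change over time is assigned to the hierarchical model. No correction family is defined, so power at a corrected level cannot be computed from the documents.

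**Conclusion.** No change is called for. The 25-to-50 step reproduces as the number needed to expect about 25 responders for a paired pre/post test with 87.6% power at d = 0.65. If 0.65 is the all-treated effect, it is a generous margin at 99.5%. Applying the rate to controls only enlarges that group, which does no harm.

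The gap is one of documentation: whose effect 0.65 is, which population the step serves, and what power exists for between-group change. Analysts following Specific Aims and Imaging data analyses would use all treated participants, the size of the seizure improvement and the hierarchical model, whatever the answer. Within-group power at about 70 evaluable per group is 72% in the least favourable case considered and 90% if non-responders change a quarter as much; both rest on assumptions outside the documents and on an uncorrected 5% level. Between-group change is the least secure comparison (46% and 65% at 70 v 70 in those two cases), so a null result there should be read with caution. That does not show that the trial is underpowered, and no figure in the plan needs correcting.

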### **3.0 Study Procedures**

#### **3.1 Study Design**

In this multi-site study, participants may be enrolled at PVAMC, RIH, and UAB. UAB will also receive referrals from BVAMC. This study aims to enroll 264 participants across the sites: 88 with PNES, 88 with PTE, and 88 with TBI without PNES or PTE. To meet recruitment goals, we will enroll both Veterans and civilians participants. Civilians will be seen at Rhode Island Hospital. All participants will be imaged at 2 time points and will complete self-reports, assessments and symptom measures as detailed in this protocol. The PNES and PTE participants will receive 12 sessions of CBT-Sz.

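### The 20% attrition allowance is taken on the 74 needed, not on those enrolled, so at that rate 88 per group leaves about 70 completers rather than 74

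*Combined protocol and SAP*

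**What the plan says.** Section 4.1 builds the group size in four steps.

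1. A core number: "we expect 25 participants per group to be sufficient to account for the possibility of a more conservative effect size (e.g., 0.65").
2. A doubling for response: "With the expected 50% responder rate to the cognitive challenge (CBT-Sz), 50 per each group (PNES, PTE, controls").
3. An addition of 24 for the two main comorbidities: "12/condition; depression / anxiety and PTSD; 50+24=74".
4. An attrition allowance, which begins "With anticipated attrition rate of up to 20" per cent. It is worked as 74 × 0.2 and given as 14 "to 15 per group".

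The section concludes that "a sample of 88 Veterans with PNES, 88 Veterans with PTE, and 88 Veterans with TBI but no PNES/PTE can address the study hypotheses" and allow adjustment for confounders. Section 3.1 (Study Design) carries the figure forward: "This study aims to enroll 264 participants across the sites: 88 with PNES, 88 with PTE, and 88 with TBI without PNES or PTE". The Study Design Overview and section 3.6 also use 88. No other section gives a different attrition allowance or a lower target for completers.

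**The concern.** The plan treats 74 as the number per group that should remain once losses have occurred. An allowance for losses must then be worked on the number enrolled, because that is the population from which people are lost. The plan works it on the number that should be left at the end. It also takes the lower end of its own rounded range, since 88 − 74 = 14 while the product is 14.8.

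If this is right, the trial enrols its full target, loses the share it expected to lose at most, and still ends below the number on which its sample-size claim rests. The shortfall must then come from the 50 meant for the within-group and between-group comparisons, from the 24 meant for comorbidity control, or from both.

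**Working it through.** **Inputs, all from section 4.1:** core number 25 per group at an effect size of 0.65; responder rate 50%; comorbidity addition 24; attrition up to 20%; enrolment 88 per group; two-sided 5% significance level. The total of 264 is from section 3.1.

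**The plan's own figure**

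- Requirement: 25/0.5 = 50; 50 + 24 = 74.
- Allowance as the plan works it: 74 × 0.2 = 14.8, shown there as a range of 14 to 15.
- Enrolment: 74 + 14 = 88, and 3 × 88 = 264. This reproduces the plan.
- Rounding 14.8 up under the same method gives 74 + 15 = 89.

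**Correct inflation**

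- n enrolled = n needed / (1 − attrition) = 74/0.80 = 92.5, so 93 per group.
- 3 × 93 = 279, which is 15 more than 264.
- Check: 93 × 0.8 = 74.4.

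**What 88 delivers**

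- At 20% attrition: 88 × 0.8 = 70.4, so about 70 per group. Shortfall 74 − 70 = 4 per group, 12 in all.
- With 89 enrolled: 89 × 0.8 = 71.2. The rounding therefore explains less than one completer, and the wrong base explains the rest.
- Break-even attrition: 1 − 74/88 = 14/88 = 15.9%.
- If each participant were lost independently with probability 0.2 (an assumption made here), the binomial probability that a group of 88 ends with fewer than 74 completers is about 79%.

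**Effect on power** (noncentral t, two-sided 5%, effect size 0.65, no multiplicity adjustment)

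| Comparison | As planned | At 20% attrition |
|---|---|---|
| Two-sample, per group | n = 74: 97.5% | n = 70: 96.8% |
| Paired, responders only, whole shortfall charged to the core 50 | 50 × 0.5 = 25: 87.6% | 46 × 0.5 = 23: 84.6% |

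If the shortfall is charged to the comorbidity addition instead, 24 becomes 20, that is 10 per condition in place of 12. No power can be attached to that change, because the plan gives no calculation behind 12 per condition.

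The section on imaging data analyses says that results will be corrected for multiple comparisons, so these unadjusted powers are upper values. As a check on the method, the plan's other figure (14 participants, effect size 0.88, paired test, about 85% power) comes out at 86.0%.

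**The case against.** The strongest reply accepts the division and disputes its weight.

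- **Twenty per cent is a ceiling.** The shortfall of 4 is the worst case within the stated range, and it vanishes at 15.9% or below. This is true, but an allowance is meant to hold at the bound it names.
- **Seventy-four is an informal sum.** It is not the output of one power formula, no power is stated for it, and the responder doubling is applied even to controls, who receive no CBT-Sz. This stands as a limit on how much a loss of 4 can mean. It remains the only requirement that the plan gives.
- **The plan shows a range.** It prints 14 to 15, so the rounding is open. That is fair, and the rounding is worth only one enrolled participant.
- **Not every analysis loses the 20%.** Hypothesis 1 concerns the baseline scan, so later dropout need not reduce it; at 88 per group the two-sample power is 99.0%. Section 4.3 asks people who do not start or finish CBT-Sz to attend the second scan, so stopping therapy does not always mean losing imaging data. Both points reduce the practical effect. Neither is used in the plan to justify 88, and the second does not help the control group.
- **The power cost is minor.** Even the less favourable paired figure, 84.6%, is close to the 85% that the plan quotes elsewhere. This stands.

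**Conclusion.** The concern holds. At its own upper attrition rate, the stated enrolment of 88 per group leaves about 70 completers, 4 fewer per group and 12 fewer in all than the 74 per group that the plan derives. Meeting 74 at 20% loss would take 93 per group.

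The conclusion rests on two readings: that 74 is the number to be retained, and that 20% is the rate the allowance is meant to cover. Section 4.1 supports both. The power figures further assume an effect size of 0.65 and an unadjusted 5% level.

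The consequence is modest: under one percentage point of two-sample power, or about 3 points of paired power if the whole shortfall falls on the core comparison. The statement should be corrected, but the error gives no reason to change the design.

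**What to change.** Keep 88 per group and correct the closing sentence of section 4.1. The simpler wording says that 88 enrolled per group gives about 70 completers at 20% attrition, and gives the power for 70 with its assumptions. It should also say whether the shortfall of 4 is taken from the 50 or from the 24.

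The other wording says that 88 gives 74 completers provided attrition does not exceed 15.9%. It is arithmetically sound, but it replaces the plan's 20% with a lower limit, so it would need a reason to expect that retention.

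The cost is one sentence and a slightly less favourable evaluable number. Raising enrolment to 93 per group (15 more participants in all) would also remove the inconsistency, but the small effect on power does not require it.
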